1 PROTOCOL SUMMARY

Title:	Prospective, Multi-Center Clinical Study of the COVERA™ Arteriovenous (AV) Stent Graft in the Treatment of Stenosis at the Graft-Vein Anastomosis of AV Graft Circuits																																											
Sponsor:	Bard Peripheral Vascular, Inc. [name]																																											
Objective:	The objective of this study is to assess the safety and effectiveness of the COVERA™ Vascular Covered Stent for the treatment of stenotic lesions at the graft-vein anastomosis of hemodialysis patients dialyzing with a synthetic AV graft.																																											
Design & Overview:	
This is a prospective, multi-center, non-randomized, single-arm clinical study designed to assess the safety and effectiveness of the COVERA™ Vascular Covered Stent for the treatment of stenotic lesions at the graft-vein anastomosis of hemodialysis subjects with a synthetic AV graft. Safety and effectiveness measures of subjects receiving the COVERA™ Vascular Covered Stent will be compared to Performance Goals (PG) derived from the results reported in clinical literature as well as those of other prospective pivotal and post-market studies.
 
Follow-up for all treated subjects will be performed at hospital discharge, 30 and 90 days, as well as 6, 12, 18, and 24 months post-index procedure.
																																											
Study Device:	
The COVERA™ Vascular Covered Stent is a highly flexible self-expanding endoprosthesis comprised of expanded polytetrafluoroethylene (ePTFE) encapsulating a nitinol (nickel-titanium alloy) stent framework. The inner lumen of the stent graft (blood contacting surface) is carbon impregnated.
 
The COVERA™ Vascular Covered Stent is available in a straight and a flared configuration. Devices will come on either an 8F or 9F system.
 
Table 1: COVERA™ Vascular Covered Stent Sizes
 
  
 Covered Stent Outer Diameter (mm)	Covered Stent Length (mm)	Endovascular System Length (cm)	
 
 30*	40	60	80	100	
   
 6	✓	✓	✓	✓	✓	80 and 120	
 
 7	✓	✓	✓	✓	✓	
 
 8	✓	✓	✓	✓	✓	
 
 9	✓	✓	✓	✓	✓	
 
 10	✓	✓	✓	✓	✓	
  
 
* Note: only the straight configuration of the implant is available in 30mm length.
	Covered Stent Outer Diameter (mm)	Covered Stent Length (mm)					Endovascular System Length (cm)	30*	40	60	80	100	6	✓	✓	✓	✓	✓	80 and 120	7	✓	✓	✓	✓	✓	8	✓	✓	✓	✓	✓	9	✓	✓	✓	✓	✓	10	✓	✓	✓	✓	✓
Covered Stent Outer Diameter (mm)	Covered Stent Length (mm)					Endovascular System Length (cm)																																						
	30*	40	60	80	100																																							
6	✓	✓	✓	✓	✓	80 and 120																																						
7	✓	✓	✓	✓	✓																																							
8	✓	✓	✓	✓	✓																																							
9	✓	✓	✓	✓	✓																																							
10	✓	✓	✓	✓	✓																																							
Enrollment:	Enrollment will continue until a total of one-hundred nine (109) subjects are treated with the COVERA™ Vascular Covered Stent. All subjects will be followed for 24 months post index procedure.																																											
Investigational Sites:	Up to 30 investigational sites in the United States (US).																																											
Study Population:	Male or non-pregnant female ≥ 21 years of age with an expected lifespan sufficient to allow for completion of all study procedures. Eligible subjects will have a synthetic AV access graft with a hemodynamically significant stenosis at the graft-vein anastomosis.																																											

Inclusion Criteria:	
Clinical Inclusion Criteria
 
1. Subject must voluntarily sign and date the Informed Consent Form (ICF) prior to collection of study data or performance of study procedures.2. Subject must be either a male or non-pregnant female ≥ 21 years of age with an expected lifespan sufficient to allow for completion of all study procedures.3. Subject must be willing to comply with the protocol requirements, including clinical and telephone follow-up.4. Subject must have a synthetic AV access graft located in an arm that has been implanted for ≥ 30 days and must have undergone at least one successful dialysis session prior to the index procedure. 
Angiographic Inclusion Criteria
 
5. Subject must have angiographic evidence of a stenosis $\geq 50\%$ (by visual estimation) located at the graft-vein anastomosis of the subject's synthetic AV access graft and present with clinical evidence of graft dysfunction at the synthetic AV graft-vein anastomosis.6. The target lesion must be ≤ 9cm in length. Note: multiple stenoses may exist within the target lesion.7. The reference vessel diameter of the adjacent non-stenotic vessel must be between 5.0 and 9.0mm.
Exclusion Criteria:	
Clinical Exclusion Criteria
 
1. The subject is dialyzing with an AV fistula.2. The hemodialysis access is located in the lower extremity.3. The subject has an infected AV access graft or uncontrolled systemic infection.4. The subject has a known uncontrolled blood coagulation/bleeding disorder.5. The subject has a known allergy or hypersensitivity to contrast media which cannot be adequately pre-medicated.6. The subject has a known hypersensitivity to nickel-titanium (Nitinol) or tantalum.7. The subject has another medical condition, which, in the opinion of the Investigator, may cause him/her to be non-compliant with the protocol, confound the data interpretation, or is associated with a life expectancy insufficient to allow for the completion of study procedures and follow-up.8. The subject is currently participating in an investigational drug or another device study that has not completed the study treatment or that clinically interferes with the study endpoints. Note: Studies requiring extended follow-up visits for products that were investigational, but have since become commercially available, are not considered investigational studies. 
Angiographic Exclusion Criteria
 
9. Additional stenotic lesions ($\geq 50\%$) in the venous outflow that are > 3cm from the edge of the target lesion and are not successfully treated (defined as $< 30\%$ residual stenosis) prior to treating the target lesion.10. An aneurysm or pseudoaneurysm is present within the target lesion.11. The location of the target lesion would require the COVERA™ Vascular Covered Stent be deployed across the elbow joint.12. The target lesion is located within a stent or stent graft.13. The location of the target lesion would require that the COVERA™ Vascular Covered Stent be placed in the central veins (subclavian, brachiocephalic, Superior Vena Cava (SVC)) or under the clavicle at the thoracic outlet.14. There is incomplete expansion of an appropriately-sized angioplasty balloon to its

	expected profile, in the operator's judgment, during primary angioplasty at the target lesion prior to implantation of the study device.
Procedures:	All subjects will undergo a clinical evaluation at screening (prior to index procedure); treated subjects will undergo a clinical evaluation prior to hospital discharge. A telephone screen to the subject and the dialysis center will be performed at all follow-up visits.
Primary Endpoints:	The primary effectiveness endpoint of the study is an effectiveness measure based on Target Lesion Primary Patency (TLPP) through 6-months post index procedure. The primary effectiveness endpoint will be evaluated against a performance goal (PG) of 40%. The primary safety endpoint is a safety measure based on safety through 30 days post index procedure. The primary safety endpoint will be evaluated against a PG of 88%.
Secondary Endpoints:	Secondary Endpoints without Hypothesis Testing 
• TLPP through 30 days, 90 days, 12 months, 18 months, and 24 months.• Access Circuit Primary Patency (ACPP) through 30 days, 90 days, 6 months 12 months, 18 months, and 24 months.• Rate of device and procedure related AEs involving the AV access circuit through 90 days, 6 months, 12 months, 18 months, and 24 months.• Total Number of AV Access Circuit Reinterventions through 30 days, 90 days, 6 months, 12 months, 18 months, and 24 months.• Total Number of Target Lesion Reinterventions through 30 days, 90 days, 6 months, 12 months, 18 months, and 24 months.• Index of Patency Function (IPF) evaluated at 30 days, 90 days, 6 months, 12 months, 18 months, and 24 months.• Index of Patency Function – Target Lesion (IPF-T) evaluated at 30 days, 90 days, 6 months, 12 months, 18 months, and 24 months.• Secondary Patency evaluated through 30 days, 90 days, 6 months, 12 months, 18 months, and 24 months.• Acute Technical Success.• Acute Procedure Success (Anatomic and Clinical Success).
Lead Principal Investigator:	[name]. Interventional Radiology The Palo Alto Medical Foundation [name] [contact]

2 STATISTICAL ANALYSIS PLAN

2.1 Overview of Study Design

The clinical study will be a prospective, multi-center, non-randomized, single-arm study with the primary objective to demonstrate the effectiveness and safety of the COVERA™ Vascular Covered Stent for treatment of lesions at the graft-vein anastomosis of patient's dialyzing with synthetic AV grafts.

2.2 Analysis populations

The analysis populations will be defined as follows for this study:

- The ITT population will consist of all subjects that have met all eligibility criteria, undergone successful PTA of the target lesion, and into which the COVERA™ Vascular Covered Stent System is introduced (i.e. the delivery system enters the subject's body).

Subjects who do not receive the study device, but into which the COVERA™ Vascular Covered Stent System was introduced, will be included in the ITT population. Subjects who require additional treatment modalities will be included in the ITT population.

- The Modified ITT (MITT) population will consist of any subjects in the ITT population who are treated with the COVERA™ Vascular Covered Stent (following PTA).
- A Per-Protocol (PP) population may be created if there are subjects who have any major protocol deviations. The PP population will consist of any subjects in the MITT population who do not have any major protocol deviation. The protocol deviations that are considered to have a "major" grade will be defined a priori in the analysis plan.

All analyses including the primary analyses will be primarily based on the MITT population. Key safety analysis will be performed based on ITT population as well. PP analyses may also be performed for the primary endpoints. They will only serve as sensitivity analyses for the primary analyses which are based on the MITT population.

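### As written, a subject who receives the stent but is later found ineligible, or whose PTA is judged unsuccessful, falls in no analysis set, including the one for the key safety analysis

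*Combined protocol and SAP*

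**What the plan says.** Section 2.2 of the SAP defines three populations, each inside the one before.

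- ITT: "The ITT population will consist of all subjects that have met all eligibility criteria, undergone successful PTA of the target lesion", and in whom the delivery system entered the body. Subjects in whom the system was introduced but the device not implanted are expressly kept.
- MITT: "will consist of any subjects in the ITT population who are treated with the COVERA™ Vascular Covered Stent".
- PP (optional): "The PP population will consist of any subjects in the MITT population who do not have any major protocol deviation".

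Their use is stated in the same section: "All analyses including the primary analyses will be primarily based on the MITT population", and "Key safety analysis will be performed based on ITT population as well". PP serves only as a sensitivity analysis for the primary endpoints. No safety, as-treated or all-enrolled set is named.

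The Protocol Summary sets enrollment without an eligibility condition: "Enrollment will continue until a total of one-hundred nine (109) subjects are treated with the COVERA™ Vascular Covered Stent". Section 2.7 summarizes all secondary endpoints, including Acute Technical Success and Acute Procedure Success, on MITT.

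**The concern.** An ITT or safety population normally catches everyone exposed to the device, and narrower sets are then cut from it. Here the widest set already carries the eligibility and PTA conditions, so anyone who fails either is removed before the narrower sets are formed. Three things follow.

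- A device-exposed subject can be missing from every planned safety result because of how that subject was classified.
- PP cannot show the effect of eligibility deviations, because those subjects never reach MITT.
- MITT can be smaller than the 109 treated for a reason that section 2.5 does not allow for; it allows for attrition only.

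In an open single-arm study against a fixed goal, set membership should not depend on a judgement that could be made after the outcome is known. The text supplied does not say when ITT eligibility is fixed, and it does not define success of the target-lesion PTA. The residual-stenosis threshold in exclusion 9 applies to additional lesions in the venous outflow.

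A related, conditional point concerns acute success. MITT holds only implanted subjects. If technical success requires implantation, MITT cannot record a failed deployment.

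**Working it through.** **Set membership.** Take a subject who was implanted and later found not to meet a criterion.

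- Counted among the 109 treated (Protocol Summary, Enrollment): yes.
- ITT: no, because all eligibility criteria must be met.
- MITT: no, because it is a subset of ITT.
- PP: no, because it is a subset of MITT.
- Key safety analysis: no, because it uses ITT.

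A subject whose PTA is judged unsuccessful follows the same path. The missing-data rules in section 2.4 do not recover either subject: they deal with missing endpoints, not with exclusion by definition.

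**The plan's own safety figure.** Inputs from sections 2.5 and 2.6.4: 109 treated, 5% attrition by day 30, assumed rate 98%, goal 88%, exact binomial test, one-sided p<0.05.

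- Evaluable: 109 × 0.95 = 103.55, so 104, as stated.
- Smallest passing count at n=104: 98 event-free (6 events), since P(X≥98 | 104, 0.88) = 0.0274 and P(X≥97 | 104, 0.88) = 0.0587.
- Power at 98%: 0.995, consistent with the stated 99%.

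**Can an exclusion change the decision?** The test allows 6 events at every n from 96 to 106, and 7 at n from 107 to 109.

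- At 104 evaluable, dropping up to 8 subjects leaves the allowance at 6, so it can only turn a fail into a pass. 97/104 fails (p=0.0587). Without one excluded subject who had an event, 97/103 passes (p=0.0295).
- With more evaluable subjects it can go the other way. 102/109 passes (p=0.0420). Without three event-free subjects, 99/106 fails (p=0.0514).

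**How likely is the fail-to-pass flip at 104?** Suppose exactly one implanted subject is excluded and carries the same event risk as the others (assumption). The flip needs exactly 7 events in 104, and the excluded subject must be one of the 7:

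P(flip) = P(exactly 7 events in 104) × 7/104

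| True event-free rate | P(exactly 7) | × 7/104 | P(flip) |
|---|---|---|---|
| 98% (plan) | 0.0038 | 0.0673 | about 0.03% |
| 95% (assumed) | 0.1146 | 0.0673 | about 0.8% |

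Both are conditional on such a subject existing. The documents give no expected number.

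**Acute success.** Assume that technical success requires implantation and that all 109 implanted subjects are successes. The MITT rate is then 109/109 = 100%. On all introduced subjects, with illustrative counts of non-implanted subjects:

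- 1 not implanted: 109/110 = 99.1%
- 2 not implanted: 109/111 = 98.2%
- 5 not implanted: 109/114 = 95.6%

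**The case against.** The strongest reply is that the literal reading is not what was meant. Section 2.2 creates PP for subjects with major deviations, to be defined a priori, and eligibility violations are an obvious candidate. The authors may have expected such subjects to stay in MITT and leave only at PP. That is plausible, but the ITT wording as it stands removes them first, and a programmer following the SAP would do so.

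A second reply is that later reclassification is unlikely for the criteria that rest on judgement. Stenosis is estimated visually, and incomplete balloon expansion is assessed "in the operator's judgment, during primary angioplasty at the target lesion prior to implantation of the study device". Both are settled by the operator at the procedure, and the supplied text describes no later re-reading. This largely stands. The realistic route to the gap is a factual error found afterwards, such as graft age or a lesion inside an existing stent. A reader might infer that the sponsor could drop subjects selectively after seeing outcomes. The documents do not support that inference; they only fail to say when eligibility is fixed.

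Third, ITT already includes subjects in whom the device was introduced but not implanted, and a safety analysis on ITT is planned. This is correct for subjects who were eligible and successfully dilated, so there is no separate complaint about them. Whether that analysis repeats the exact test against 88% is a reporting preference.

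Fourth, Acute Technical Success and Acute Procedure Success are not defined in the supplied text. If they also cover placement accuracy or residual stenosis, MITT can still record some failures. This stands, and the acute success point is therefore conditional.

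**Conclusion.** The point holds as a defect in the set definitions. Followed as written, section 2.2 leaves an implanted subject who is ineligible or whose PTA is judged unsuccessful out of ITT, MITT and PP, and so out of all planned safety reporting. It may well be unintended.

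The main consequence is incomplete safety reporting of device-exposed subjects. A reader might infer that the 88% decision is seriously at risk, perhaps from the 0.4% (at 98%) and 11.5% (at 95%) chances of exactly 7 events in 104. Those are not flip probabilities, because the excluded subject must also be one of the 7. With one excluded subject at equal risk the chance is about 0.03% and 0.8%, and even that presupposes that such a subject exists. A higher risk or several such subjects would raise it, but the documents give no basis for a figure.

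A reader might also infer that acute success will be overstated. That depends on technical success requiring implantation and on at least one failed deployment. These endpoints are descriptive, and no pass/fail decision depends on them.

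**What to change.** 1. Add to section 2.2 a safety set of all subjects into whom the delivery system is introduced, regardless of eligibility or PTA result. Run the key safety analysis on it. Report the number and safety outcomes of implanted subjects left out of MITT.
2. Settle where eligibility failures belong. Either list them as major deviations handled at PP, with the ITT wording changed so that they reach MITT, or state that ITT eligibility is fixed at the procedure before outcomes are known. The safety set alone cures the safety reporting and leaves the population for the 40% TLPP test unchanged. The first option would bring eligibility failures into that population, so it should be a deliberate choice.
3. In section 2.7, report Acute Technical Success and Acute Procedure Success on all introduced subjects beside MITT.

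The cost is SAP wording and a little extra analysis, with no added subjects or visits. Safety and acute success figures may come out slightly less favourable.

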2.5 Sample Size Estimation

The sample size calculation assumes the following:

- 1) Primary Effectiveness Endpoint – TLPP at 6 months performance goal.
 - Assumptions:
 - The COVERA™ Vascular Covered Stent composite freedom from event rate is estimated at 55%;
 - The PG is set at 40%;
 - Attrition (drop-out) rate (by 6 months) = 15%;
 - The Type 1 error, $\alpha = 0.05$ (one-sided); and
 - The Type 2 error, $\beta = 0.10$ (Power = $1 - \beta = 90\%$).
 - Sample Size:
 - 109 treated subjects [93 evaluable] will give 90% power with one-sided type I error =0.05.
- 2) Primary Safety Endpoint – Safety at 30 days:
 - Assumptions:
 - The primary safety rate through 30 days in the study device treated subjects is 98%;
 - The PG is set at 88%;

- Attrition rate (by day 30) = 5%; and
- The Type 1 error, $\alpha = 0.05$ (one-sided).
- Sample Size:
 - 109 treated subjects [104 evaluable] will give 99% power with one-sided type I error =0.05.

Hence, the sample size of 109 subjects will provide approximately $(99\%)*(90\%)=89\%$ power for the both primary effectiveness and primary safety endpoint.

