2.6.4 Primary Safety Endpoint Hypothesis Test

The primary safety endpoint is safety through 30 days. Objective: To assess if the 30-day primary safety rate for the study device is greater than the safety PG:

H_0 : The proportion of subjects in the study device treatment group (P_{CS}) free from safety events in the primary safety endpoint is less than or equal to the safety PG of 88%.

H_1 : The proportion of subjects in the study device treatment group (P_{CS}) free from safety events in the primary safety endpoint is greater than the safety PG of 88%.

That is:

H_0 : $P_{CS} \leq 88\%$,

H_1 : $P_{CS} > 88\%$,

Rejection of the null hypothesis will signify that the 30 day safety of the COVERA™ Vascular Covered Stent is greater than the safety PG of 88%.

A one sided p-value will be derived based on an exact binomial test. The study device will be considered to have achieved the primary safety objective if the one-sided p-value is less than 0.05. Or equivalently, the lower limit of the one-sided 95% confidence limit based on exact method is greater than 88%.

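### The 88% safety goal is decided on implanted subjects only, so a subject exposed to the delivery system but left without an implant is outside the deciding test

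*Combined protocol and SAP*

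**What the plan says.** Section 2.2 of the SAP defines ITT by entry of the delivery system into the body of an eligible subject after successful PTA. It is explicit about attempts without an implant: "Subjects who do not receive the study device, but into which the COVERA™ Vascular Covered Stent System was introduced, will be included in the ITT". MITT is narrower: "The Modified ITT (MITT) population will consist of any subjects in the ITT population who are treated with the COVERA™ Vascular Covered Stent (following PTA").

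The same section assigns the decision to the narrower set: "All analyses including the primary analyses will be primarily based on the MITT population". For safety it adds: "Key safety analysis will be performed based on ITT population as well". It gives that ITT analysis no success criterion and does not say what follows if ITT and MITT disagree.

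Section 2.6.4 is consistent with this. Its null hypothesis is that the proportion of the device-treated group "free from safety events in the primary safety endpoint is less than or equal to the safety PG of 88"%. The objective is met if the one-sided exact binomial p-value is below 0.05. Section 2.5 sizes the test on the same basis: "109 treated subjects [104 evaluable] will give 99% power with one-sided type I error =0.05".

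**The concern.** Whether a subject enters MITT depends on how the procedure went, and this is known only after the device system has entered the body. The safety endpoint runs from the index procedure, so an injury during delivery falls inside its time window. If that subject leaves without a stent, the event is outside the test that decides the safety objective. With a single arm, there is no control group in which a similar exclusion could offset this one.

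At stake is a safety goal declared met in implanted subjects when the same test in everyone exposed to the system would fail.

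**Working it through.** **Inputs.** Goal 88%, i.e. a 12% event rate under H0 (Sections 1 and 2.6.4). Assumed safety rate 98%, i.e. 2% events; 109 treated; 5% attrition; one-sided alpha 0.05 (Section 2.5). Exact binomial test (Section 2.6.4). The number of non-implanted subjects and their event rate are not given, so both are varied below. The components of the safety endpoint are not in the available text; it is assumed that delivery-related harm counts as an event.

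**Step 1: the plan's own figure.** 109 × 0.95 = 103.55, rounded to 104 evaluable. The p-value for x events in n subjects is P(X ≤ x | n, 0.12). At n = 104, 6 events give p = 0.0274 and 7 give p = 0.0587, so at most 6 events are allowed. Power is P(X ≤ 6 | 104, 0.02) = 99.5%, which agrees with the stated 99%. At n = 109 at most 7 events are allowed (p = 0.0420) and power is 99.8%.

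**Step 2: one event in a non-implanted subject.**

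| MITT events/n | p | ITT events/n | p | Verdict |
|---|---|---|---|---|
| 6/104 | 0.0274 | 7/105 | 0.0550 | MITT passes, ITT fails |
| 7/109 | 0.0420 | 8/110 | 0.0775 | MITT passes, ITT fails |
| 6/106 | 0.0236 | 7/107 | 0.0481 | both pass |

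The third row shows that the reversal does not occur at every n: the allowed count rises from 6 to 7 at n = 107.

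**Step 3: how likely the reversal is.** Suppose there is exactly one non-implanted subject, with an event. The verdicts then differ only if MITT sits on its limit.

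- True safety rate 98% in implanted subjects (the plan's assumption): P(X = 6 | 104, 0.02) = 1.3%; P(X = 7 | 109, 0.02) = 0.5%.
- True rate 95% (an assumption, not in the documents): P(X = 6 | 104, 0.05) = 15.6%; P(X = 7 | 109, 0.05) = 12.4%.

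**Step 4: error rate if the target is all exposed subjects.** Let the true event rate in all exposed subjects be exactly 12%, with 109 implanted and evaluable, and m further subjects not implanted, each with event probability q. The rate in implanted subjects is then r = (0.12 × (109 + m) − m × q) / 109, and MITT passes with probability P(X ≤ 7 | 109, r). For m = 1 and q = 1, r = (13.2 − 1)/109 = 0.1119, giving 6.9%.

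| q | m = 1 | m = 2 | m = 3 |
|---|---|---|---|
| 0 | 3.9% | 3.6% | 3.4% |
| 0.12 | 4.2% | 4.2% | 4.2% |
| 0.25 | 4.5% | 4.9% | 5.3% |
| 0.5 | 5.2% | 6.5% | 8.0% |
| 1 | 6.9% | 11.0% | 17.0% |

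**Step 5: power with ITT deciding.** If the true safety rate in all exposed subjects is 98%, exact power is 99.5% at n = 105 and 99.8% at n = 110 to 112.

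**The case against.** A reader might infer that leaving out non-implanted subjects can only help the device. That is wrong, because MITT also drops those without an event. MITT 7/106 fails (p = 0.0514); adding one event-free non-implanted subject gives ITT 7/107, which passes (p = 0.0481).

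A reader might also infer that the planned test breaks its 5% level. For the hypothesis as written, about the device-treated group, it does not: the exact level is 4.2% at n = 109. The excess appears only when the target is everyone exposed, and only when non-implanted subjects have clearly more events than implanted ones. The largest figures need every one of them to have an event.

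The plan is not silent either. The ITT safety analysis means that such events would be reported, and which population is primary is partly a choice of estimand. It is also unknown whether the 88% goal, drawn from literature and other studies, was built on attempted or on treated subjects.

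These objections limit the size of the point. They do not answer it. Reporting an ITT result is different from letting it count, and nothing in Section 2.2 or 2.6.4 lets it count. The missing-data provisions in Section 2.4, including the tipping-point analysis, deal with missing endpoints and not with subjects outside the analysis set.

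**Conclusion.** The point holds as one about which population decides the safety claim. A subject exposed to the system but not implanted cannot affect the 88% verdict, and the bias is towards the device if such subjects have more events than implanted ones. That condition is plausible but is not established by the documents.

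The size is modest under the plan's own assumptions and grows if device safety is nearer the goal. Even with one such event, a reversed verdict has a 0.5% to 1.3% chance at 98% safety, and 12% to 16% at an assumed 95%. For the all-exposed target, the false-pass rate runs from 3.4% to 17.0% over the range shown. If every introduction ends in an implant, the two tests are identical. All of this assumes that delivery-related harm is a safety event under the endpoint. The change is worth making because it removes selection on procedural success at little cost.

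**What to change.** In Sections 2.2 and 2.6.4, name ITT (every subject into whom the system was introduced) as the deciding population for the primary safety hypothesis. Restate H0 and H1 as the proportion of ITT subjects free from primary safety events through 30 days, at most 88% versus above 88%. Report MITT as supportive.

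State that 30-day safety outcomes are collected for non-implanted ITT subjects. Section 1 gives the follow-up schedule and the pre-discharge evaluation for treated subjects only, so these data are not clearly secured, and the ITT safety analysis already planned needs them. Confirm from the source of the 88% goal that it suits an attempted-subject denominator.

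The cost is a few sentences of wording, 30-day follow-up of a few extra subjects, and a reported safety rate that may be slightly lower. No extra treated subjects are needed. Exact power stays above 99% if the 98% rate applies to all exposed subjects. If one non-implanted subject with an event is taken as given and implanted subjects have a 98% rate, the ITT test passes with probability 98.2% (P(X ≤ 5 | 104, 0.02)) or 99.4% (P(X ≤ 6 | 109, 0.02)).
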